lower ratio of *Firmicutes* to *Bacteroidetes*, which are some of the most abundant bacterial phyla present in the human gut [8]. Some studies suggest that the altered intestinal microflora profile of obese individuals may lead to an increase in production of lipopolysaccharide (LPS) endotoxin, which is derived from the cell wall of gram-negative bacteria in the gut (such as the *Bacteroidetes* mentioned earlier) and induces an inflammatory response by the body [9]. This may be one reason why overweight and obese individuals often present elevated levels of inflammatory markers in the blood, including LPS [10] and other more established markers of inflammation such as C-reactive protein (CRP) [11].

The composition of the intestinal bacteria is influenced by several factors, including host genotype, age, sex, antibiotic/medication use, disease, and diet. Changes in the intake of specific food components may lead not only to changes in the gut bacteria but may also lead to changes in gene expression of different tissues in the host, which may be directly related to more or less fat storage [12]. For example, a cross-over study looking at the effects of consumption of 4 weeks of fermented kimchi and 4 weeks of fresh kimchi in obese Korean subjects (7 male and 15 female) found significant decreases in body weight, and body fat after consumption of fermented and fresh kimchi. In addition, decreases in blood pressure, percent body fat, fasting glucose, and total cholesterol were significantly greater during the fermented kimchi phase compared with the fresh kimchi phase [13]. In a parallel arm study conducted with overweight and obese Korean women, consumption of both fermented and fresh kimchi resulted in a decrease in the *Firmicutes* to *Bacteroidetes* ratio and in the relative abundance of *Bifidobacteria*, even though there were no significant differences between groups in body weight or inflammatory markers [14]. The findings from these Korean studies suggest that fresh and fermented kimchi may have different effects on intestinal bacteria and metabolism of the host. Unfortunately, very few studies examining the effects of fermented foods on metabolic parameters have been conducted in the U.S., likely due to the low consumption of fermented vegetables by the population. The present study was designed to investigate

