the effects of fermented vegetables on the composition of the gut microflora and other biological and clinical parameters associated with obesity and other chronic diseases.

Study Aims

Aim 1: To examine the effect of daily consumption of fermented vegetables compared with non-fermented vegetables for 6 weeks on markers of metabolic syndrome and inflammation of overweight and obese women.

Hypothesis 1: Consumption of fermented vegetables will improve markers of metabolic syndrome (blood pressure, insulin, adiposity) and inflammation, such as C-reactive protein (CRP), and lipopolysaccharide (LPS) in overweight and obese women.

Aim 2: To examine the effect of daily consumption of fermented vegetables compared with non-fermented vegetables for 6 weeks on the profile of the gut microflora.

Hypothesis 2: Consumption of fermented vegetables will lead to a shift in microbial communities towards an increase in communities regarded as probiotics such as Bifidobacteria and Lactobacilli.

Significance

Obesity continues to be a major public health burden and its consequences have a significant impact on disease risk and quality of life, particularly in women who are more affected by this problem than men. Several weight loss interventions have been tested in the past 30 years, but it does not seem that a great impact in obesity treatment has been made so far. This is partially due to the fact that weight loss trials have a transient positive effect, which gets reversed as soon as the intervention stops. Due to these challenges faced by traditional weight loss trials, there is a need to look for alternative approaches to reduce the burden of obesity, particularly in women. Although it is now well recognized that there is a

strong relationship between the gut bacteria and obesity, there is a lack of feeding studies aimed at altering the composition of the gut bacteria via consumption of fermented foods. In addition, most of the studies examining the effects of fermented foods on health and disease parameters have been conducted in Asian countries, where the consumption of fermented foods like kimchi and soy products is high compared with Western countries. This proposal addresses the gap in the research with fermented foods that exists in the U.S. by examining the effects of consumption of fermented vegetables on several markers associated with obesity in women.

Methodology and analysis

Methodology

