Study design: This will be a parallel arm study where 39 women will be randomized into one of three treatment groups: a fermented vegetable group (n=13), a non-fermented vegetable group (n=13), and a control group (n=13). The duration of the study will be 6 weeks and women in the vegetables groups will be asked to consume 1 cup of vegetables (140 g) per day for the entire duration of the study as well as follow their usual diet. Women randomized into the control group will be asked to follow their usual diet. Biological samples including feces and blood samples will be collected at baseline, before randomization and at the end of the 6-week intervention.

Study participants: Thirty-nine overweight and obese women aged 20-59 years will be recruited for this study. The table below shows inclusion and exclusion criteria for the study:

INCLUSION CRITERIA	EXCLUSION CRITERIA
BMI: 26-40 kg/m ²	BMI < 26 kg/m ²
Non-smoker	Smoker

No previous diagnosis of cancer	Taking medications that affect appetite or body weight
No thyroid disease	Uncontrolled Hypertension
No diabetes	Diabetes
Willing to consume 1 cup of vegetables daily for 6 weeks	Not willing to consume 1 cup of vegetables daily for 6 weeks
No use of psychotic or depression medication	Willing to show up at two appointments
No medication to lose weight	Following a fad diet
Not on a weight loss diet	Using antibiotics frequently
No use of antibiotics over the past 3 months	Diagnosed with autoimmune disease, like psoriasis, rheumatoid arthritis, thyroid disease, colitis
No consumption of fermented vegetables on a regular basis	Regular consumption of fermented vegetables
No history of autoimmune disease, including gastrointestinal disease	

Study procedures: Participants will be recruited by posting flyers at UNF Women's Center and in Jacksonville Women's clinics, as well as by newspaper advertisements. Interested participants will be asked to contact the study via email sent to an email account that will be created for the study. Upon receiving emails from interested participants, study staff will conduct a screening interview to ensure eligibility for the study. If women are found to be eligible after the initial screening interview, a screening clinic visit for verification of eligibility status will be scheduled. At the screening clinic visit all the study

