Treatment groups will be compared at both times points using analysis of variance. Changes from baseline within treatment groups in clinical and laboratory measures will be compared by paired *t* tests. Pearson's correlation coefficients will also be calculated between clinical and laboratory parameters and alterations in the intestinal microflora.

Plan for dissemination of results

The findings from this project will be disseminated in three different ways: via open access peer-reviewed manuscripts, poster presentations at scientific meetings, and via UNF newspaper. It is also expected that this project will originate pilot data to apply for external funding from institutions such as the Obesity Society and the American Heart Association.

Timeline

Project activities	Year 1				Year 2			
	Q1	Q2	Q3	Q4	Q1	Q2	Q3	Q4
IRB application and approval								
Recruitment and enrollment of participants								
Intervention/data collection								

Sample preparation for analysis and shipping							
Intestinal microflora analysis at St. Could State University							
Statistical analysis							
Manuscript preparation and dissemination							

Project budget (\$14,975.65)

Undergraduate research assistant (\$1,431.75)

I am requesting funds to hire an undergraduate student for 7 hours per week to help with recruitment and the intervention for 19 weeks at \$10/hr. ($\$10 * 19 * 8 = \$1330 + 7.65\% = \$1,431.75$).

Graduate student (nurse practitioner) (\$280)

I would like to hire nurse practitioner students for the blood draws. I estimate that each blood draw will take 15 minutes, which adds up to 10 hours for 39 participants before and 10 hours after the intervention for a total of 20 hours. ($\$13/h for 20 hours = \$260 + 7.65\% = \$280$)

Laboratory supplies

Assay kits for assessment of blood markers (\$2,362)

CRP: 1 kit for 36 samples at \$479, need 2 kits = \$958, Insulin: 1 kit for 36 samples at \$449, need 2 kits = \$898, LPS: 1 kit for 36 samples at \$253, need 2 kits - \$506

Blood and stool collection supplies (\$433)

Needles, tubes, tourniquets: \$150, Tubes to store serum in ultracold freezer: \$159, Stool collections cups and hats: \$108, Tongue depressors: \$16

Microflora analysis (\$8,500)

DNA extraction of stool samples: \$900

Sequencing for identification of microflora \$1,500 per 17 samples, we will have a total of 84 samples: \$7,500

Shipping (overnight) of stool samples to Minnesota: \$100

Vegetables (\$900)

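### The planned Pearson correlations with microflora changes have no treatment-arm term, so a coefficient pooled over 39 women can mix the arm effect with the within-arm link (minor priority)

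*Combined protocol and SAP*

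**What the plan says.** The Analysis section of the combined protocol and SAP describes the correlation analysis in one sentence: "correlation coefficients will also be calculated between clinical and laboratory parameters and alterations in the intestinal microflora". The coefficient is Pearson's. No arm term, pooling rule, significance level or test is given. The sentence sets parameters against alterations, so it is open whether the clinical side is a baseline level, a final level or a change.

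The sentence before it does state its grouping: the paired t tests concern "Changes from baseline within treatment groups in clinical and laboratory measures". The correlation sentence has no such limit, and no other section supplies one.

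Study design sets the size: "a fermented vegetable group (n=13), a non-fermented vegetable group (n=13), and a control group (n=13" women, 39 in all. Hypothesis 1 expects that fermented vegetables "will improve markers of metabolic syndrome (blood pressure, insulin, adiposity) and inflammation". Hypothesis 2 expects "a shift in microbial communities towards an increase in communities regarded as probiotics such as Bifidobacteria and Lactobacilli". The dissemination plan expects that "this project will originate pilot data to apply for external funding".

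**The concern.** Hypotheses 1 and 2 together say that arm moves both the markers and the microflora. If so, arm is a common cause of both. Pooled over the 39 women, the two changes would then be correlated even if, inside every arm, a woman's change in a taxon said nothing about her change in a marker. The effect is on the coefficient itself, so it does not depend on a test being done.

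The distortion can also hide a link. If the within-arm correlation is positive and the arm shifts run in opposite directions, the pooled coefficient is pulled towards zero.

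At stake is the reading of the only planned analysis that connects microflora with clinical and laboratory measures. A pooled coefficient could be published, or used in a funding application, as evidence of a biological link when it partly restates the arm effect. Neither aim concerns this link, and the between-arm comparisons do not depend on it.

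**Working it through.** **Inputs from the documents.** Three arms of 13 women, 3 × 13 = 39 (Study design); Pearson's r (Analysis); hypothesised shifts on both variables, without sizes or SDs (Study Aims). The documents give no power calculation or expected correlation, so there is no planned figure to reproduce. Dropout is foreseen in the budget but no rate is given, so 39 and 13 are upper limits.

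**Assumptions.** Normal data, a two-sided 5% test of r, and shifts of 0.3 to 1.5 within-arm SD.

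**Critical values.** |r| must exceed t/√(df + t²), with t the 97.5% point:
- pooled, df = 39 − 2 = 37: 0.316
- adjusted for two arm indicators, df = 39 − 2 − 2 = 35: 0.325
- one arm, df = 13 − 2 = 11: 0.553

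**Expected pooled r with no within-arm link.** If one of three equal arms is shifted by d SD on both variables, the between-arm variance is (1/3)(2/3)d² = (2/9)d². The size of the large-sample r is then (2/9)d² / (1 + (2/9)d²):
- d = 0.5: 0.0556/1.0556 = 0.053
- d = 0.8: 0.1422/1.1422 = 0.125
- d = 1.0: 0.2222/1.2222 = 0.182
- d = 1.5: 0.5/1.5 = 0.333

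The factor 2/9 is the same if both vegetable arms shift against control. The sign is negative when a taxon rises and a marker falls.

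**Simulation** (3 × 13, no within-arm link, fermented arm shifted equally on both variables):

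| Shift (SD) | Mean pooled r (size) | Pooled rejection | Arm-adjusted rejection |
|---|---|---|---|
| 0 | 0 | 5% | 5% |
| 0.3 | 0.02 | 5% | 5% |
| 0.5 | 0.05 | 6% | 5% |
| 0.8 | 0.13 | 12% | 5% |
| 1.0 | 0.19 | 20% | 5% |
| 1.5 | 0.34 | about 59% | 5% |

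The mean arm-adjusted r is 0 throughout. Shifting both vegetable arms gives the same pooled rates at 0.5, 0.8, 1.0 and 1.5 SD.

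**Where the bias fades.** With the taxon shifted 1.0 SD and the marker 0, 0.3 or 0.5 SD, pooled rejection is 5%, 6% and 9%. Baseline parameters are measured before randomization, so arm cannot shift them: even with a 1.5 SD taxon shift, rejection stays at 5%.

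**Masking.** With a within-arm r of +0.4 and 1 SD shifts in opposite directions, the expected pooled r is (0.4 − 0.222)/(1.222) = 0.15. Pooled power is 12%, against 71% adjusted.

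**Power with no arm shift and the same link in every arm (r = 0.5).** Pooled 91%, arm-adjusted 90%, one arm alone 43%. With no link and no correction, the chance that at least one of three arms is significant is 14% (1 − 0.95³ = 0.143).

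**Link in the fermented arm only (r = 0.5 there, 0 elsewhere).** The adjusted r averages about 0.5/3 = 0.17, with power of about 17%, against 43% within that arm.

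**The case against.** **The harm is conditional.** The arms must be pooled, both variables must be changes or final values, and arm must shift both by a good deal. At 0.5 SD the bias of 0.05 is small beside the sampling SD of r, about 1/√38 = 0.16. The Analysis section says only that coefficients are calculated, so false-positive rates matter only if someone tests them. All of this stands and sets the priority.

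**The background does not show the needed shifts.** A reader might infer from the cited kimchi studies that large shifts on both variables are likely here. The text does not support that. The crossover study "found significant decreases in body weight, and body fat after consumption of fermented and fresh kimchi", which is change over time with both products. In a separate parallel-arm study, "consumption of both fermented and fresh kimchi resulted in a decrease in the" Firmicutes to Bacteroidetes ratio, again with both products. No untreated control is mentioned for either. The parallel-arm study is the one described as reporting both microflora and inflammatory markers, and it found no significant between-group marker difference. It also reported a fall in Bifidobacteria, opposite to Hypothesis 2; the sign does not alter the size of the bias. The case for shifts on both variables therefore rests on the trial's own hypotheses.

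**Thirteen women per arm is not an error.** A reader might take by-arm analysis as a second fault. By-arm coefficients carry no arm bias. They are imprecise because the trial is small, and it is expected to yield pilot data.

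**Adjustment changes the question.** If the taxon truly carries the arm effect to the marker, between-arm variation is signal. With an assumed path of 0.4 and taxon shifts of 0.5, 1.0 and 1.5 SD, power is 71% adjusted against about 75%, 81% and 88% pooled. Adjustment also assumes one slope for all arms, and only the fermented product is described as containing live organisms. Both points stand, and are reasons to report the other coefficients as well.

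**Conclusion.** The point holds as a conditional one of minor priority. The stated method has no arm term. If it is applied to changes pooled over the 39 women, and the trial's two hypotheses are both right, the coefficient mixes the arm effect with the within-arm link. The effect is negligible at shifts of 0.5 SD or less, moderate at 0.8 to 1.0 SD, and large only near 1.5 SD on both variables. These sizes are assumptions, as are normality and the 5% test.

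A reader might conclude that the planned correlations are invalid or that the trial's main results are compromised. Neither follows: readings of the sentence by arm or with baseline parameters have no arm bias, and the between-arm comparisons are unaffected. What justifies a change is that a better-defined coefficient is available at almost no cost.

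**What to change.** Replace the correlation sentence with:

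> Over all participants with both samples, change from baseline in each clinical or laboratory measure will be correlated with change in each microflora measure by partial correlation adjusted for treatment arm (two indicators; 35 df with 39 women). Unadjusted and by-arm coefficients will be shown as descriptive. Results are exploratory.

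This settles pooling, the arm term, and level versus change together. It needs no new data and a few lines of code.

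The costs are two degrees of freedom (critical |r| 0.325 rather than 0.316; power 90% rather than 91% at r = 0.5), some power if the taxon mediates the arm effect, and the common-slope assumption. Showing the unadjusted coefficient keeps the between-arm signal visible. Showing by-arm coefficients guards against missing a link confined to the fermented arm.

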procedures will be explained in detail, and participants will be asked to sign the consent form if they agree to participate. Blood and stool samples will be collected and once all eligibility criteria are confirmed, participants will be randomized into one of the three groups and arrangements will be made for weekly pick up/delivery of vegetables to those in the vegetables groups.

Vegetables preparation: Fermented vegetables for the entire study will be provided by a local producer weekly, whereas non-fermented vegetables samples will be obtained at a local grocery store. The process of vegetable fermentation involves *Lactobacilli* and *Bifidobacteria* that are naturally found on the leaves of cabbage, carrots and on cucumbers. These bacteria are able to convert the carbohydrates present in these vegetables into lactic acid under anaerobic conditions. The lactic acid is responsible for the acidic flavor of the fermented vegetables. The non-fermented vegetables will serve as a positive control for the fermented vegetable group, because it will have a similar flavor but no live microorganisms, mainly because store-bought pickled vegetables and sauerkraut are made by a different process that uses acetic acid, instead of live bacteria. Vegetable samples will be portioned by study staff using food safety precautions and delivered to participants weekly.

Biological sample collection: Blood samples will be collected in red top tubes to obtain serum for determination of insulin, CRP, and LPS. CRP will be measured using a commercial ELISA kit (Cat#DCRP00, R&D Systems, Minneapolis, MN). LPS will be measured using Pierce LAL chromogenic endotoxin quantitation kit (Cat#88282, ThermoFisher Scientific, Waltham, MA). All analyses will be conducted in [name] laboratory, which is already set up for these measurements. Stool samples will be collected to analyze the composition of the gut bacteria. Participants will receive a stool collection kit prior to the initial screening visit and they will be asked to bring the stool sample to the screening visit.

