Commercial sauerkraut for non-fermented vegetables group (\$44.30 per 384 oz – need 223 oz per person for the entire study, $223 \times 13 \text{ people} = 2899 \text{ oz} = 8 \text{ cases}$): \$355

Fermented vegetables (\$29 per 256 oz – need 223 oz per person for the entire study): \$377

Storage containers: (need 1 cup containers: 42 days \times 39 participants = 1638 containers, \$24 per case of 240, need 7 cases): \$168

Participant compensation (\$780)

\$20 dollars for completing the study, \$5 for completing baseline measures and \$15 for completing the 6 weeks. Compensation will be pro-rated if participants drop out before 6 weeks.

Car mileage (\$288.90)

Vegetables samples will be delivered to participants weekly for 6 weeks. Assuming that we will drive 15 miles for every 5 participants per week = 15 miles \times 6 (28 participants in the vegetables groups divided by 5 = 6) \times 6 weeks = 540 miles \times \$0.535 = \$288.90

Bibliography

2. Ogden, C. L., Carroll, M. D., Fryar, C. D., and Flegal, K. M. (2015) Prevalence of obesity among adults and youth: United states, 2011-2014. *NCHS Data Brief* **(219)**, 1-8.
3. Bradlow, H. L. (2014) Obesity and the gut microbiome: Pathophysiological aspects. *Hormone Molecular Biology and Clinical Investigation* **17**, 53-61.
5. Turnbaugh, P. J., Ley, R. E., Mahowald, M. A., Magrini, V., Mardis, E. R., and Gordon, J. I. (2006) An obesity-associated gut microbiome with increased capacity for energy harvest. *Nature* **444**, 1027-1031.

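### The vegetables in the two vegetable arms are neither specified nor required to match, and sauerkraut is the only comparator food costed

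*Combined protocol and SAP*

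**What the plan says.** Study Aims sets the contrast. Aim 1 studies fermented vegetables "compared with non-fermented vegetables for 6 weeks on markers of metabolic syndrome and inflammation", and Aim 2 studies them "compared with non-fermented vegetables for 6 weeks on the profile of the gut microflora".

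Study design gives both vegetable arms one cup (140 g) a day for 6 weeks, with 13 women per arm. There is a third arm: "Women randomized into the control group will be asked to follow their usual diet".

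Vegetables preparation describes the two foods:

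- On the fermented side, "Fermented vegetables for the entire study will be provided by a local producer weekly". The fermenting bacteria are described as "naturally found on the leaves of cabbage, carrots and on cucumbers".
- The comparator comes from a local grocery store. It is called a positive control "because it will have a similar flavor but no live microorganisms", and the reason given is that "store-bought pickled vegetables and sauerkraut are made by a different process that uses acetic acid".

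Project budget, Vegetables costs one comparator food, "Commercial sauerkraut for non-fermented vegetables group". The fermented line names no vegetable. Both lines allow 223 oz per person.

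**The concern.** A comparison of fermented with non-fermented vegetables is most informative about fermentation when the vegetables are otherwise alike. The plan's background gives two reasons to care. It says that changes in particular food components may change gut bacteria and host gene expression. It also reports that fresh as well as fermented kimchi was followed by shifts in gut bacteria. Both kimchi studies it cites compared fresh and fermented forms of one named food. This plan states no equivalent match.

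If the local producer supplies a mix and the comparator arm eats sauerkraut, every woman in one arm gets one set of vegetables and every woman in the other gets another. A difference between the arms, or the lack of one, could then reflect the vegetables as well as the fermentation. Randomization would still support a fair comparison of the two products, but not the attribution to fermentation that a reader is likely to make.

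**Working it through.** **Step 1: how much of the comparator arm the sauerkraut covers.** The inputs are from Project budget, Vegetables: 223 oz per person, 13 people, 384 oz per case at $44.30.

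- Need: 223 × 13 = 2,899 oz, as stated.
- Cases: 2,899 / 384 = 7.55, rounded up to 8, as stated.
- Cost: 8 × $44.30 = $354.40, stated as $355.
- Coverage: 8 × 384 = 3,072 oz, and 3,072 / 2,899 = 106.0%. Seven cases hold 2,688 oz, or 92.7%.

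Sauerkraut is therefore costed for the whole arm. This does not depend on the 223 oz. If ounces are read as weight, 140 g × 42 days = 5,880 g, about 207.4 oz per person, or about 2,696 oz for 13. Eight cases still cover it, and seven cover about 99.7%.

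**Step 2: whether another line could pay for a different comparator vegetable.**

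- Vegetables heading: 355 + 377 + 168 = $900, as stated.
- All eight headings: 1,431.75 + 280 + 2,362 + 433 + 8,500 + 900 + 780 + 288.90 = $14,975.65, equal to the stated total.

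No other line holds comparator food, and nothing is unallocated.

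**Step 3: what is specified about each arm's food.**

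| Feature | Fermented arm | Comparator arm | Status |
|---|---|---|---|
| Portion and duration | 140 g/day, 6 weeks | 140 g/day, 6 weeks | Matched |
| Budgeted amount | 223 oz per person | 223 oz per person | Matched |
| Flavor | Acidic | Said to be similar | Asserted |
| Live microorganisms | Present | Absent | Intended difference |
| Source | Local producer | Grocery store | Disclosed difference |
| Acidifying process | Lactic fermentation | Acetic acid | Disclosed difference |
| Vegetables and proportions | Not stated | Not stated in the methods; sauerkraut costed | Not specified, not required to match |

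**Step 4: what the three arms can separate.** As a simple additive sketch, let v be the effect of the vegetables eaten, p that of the process (fermented or acid-pickled) and s that of the source, each relative to usual diet.

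- Fermented minus control = v(fermented) + p(fermented) + s(producer)
- Comparator minus control = v(comparator) + p(pickled) + s(store)
- Fermented minus comparator = [v(fermented) − v(comparator)] + [p(fermented) − p(pickled)] + [s(producer) − s(store)]

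The first bracket vanishes only if the vegetables are the same. Otherwise it cannot be estimated, because the control arm receives no study vegetables and no arm crosses vegetable type with process. The analysis of variance in the Analysis section estimates the sum of the brackets. More participants would estimate that sum more precisely without splitting it. The only product test planned, under Microflora analysis, concerns bacteria and would not record the vegetable mix.

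**The case against.** The strongest reply is that no mismatch has been shown. The budget is a costing, not a product specification, and it is loose elsewhere: it counts 28 women in the vegetable groups where the design has 26. A flavor-similar store product without live microorganisms is a disclosed and reasoned comparator for a project of this size, which is expected to yield pilot data. The Aims compare foods and do not explicitly claim to isolate fermentation. Matching the vegetables would still leave the source and acid differences.

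Most of this stands, and it rules out several stronger readings that a reader might infer:

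- *That one arm gets a cabbage, carrot and cucumber mix and the other only sauerkraut.* The three vegetables are named as where the bacteria occur, not as the delivered recipe. The fermented product could be cabbage alone.
- *That the methods and the budget contradict each other.* The methods mention pickled vegetables as well as sauerkraut. They are broader than the budget line, not in conflict with it.
- *That the arms match on nothing but flavor and the absence of live microorganisms.* Portion, duration and amount are matched too, and live microorganisms are the intended difference.
- *That matching the vegetables would isolate fermentation.* It removes one of several differences that coincide with arm.

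The reply does not remove the gap. Nothing in the plan prevents a vegetable mismatch, and the one comparator purchase it describes would create one unless the fermented product is cabbage alone.

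**Conclusion.** The point holds as a gap in the specification of the comparator, with a conditional consequence. The documents establish that neither arm's vegetables are specified or required to match, and that commercial sauerkraut is costed for the full comparator requirement (106% of 2,899 oz).

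The consequence needs two assumptions: that the comparator is bought as costed, and that the local producer's product is not cabbage alone. If both are true, vegetable type is inseparable from fermentation in the comparison that both Aims name. The documents do not say whether the second is true, and they give no basis for sizing any effect on the outcomes. The ounces measure how completely sauerkraut fills the comparator arm; they do not measure bias.

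This is more than a missing detail, because a comparator matched on vegetables is a concrete improvement that can be arranged before the food is bought.

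**What to change.** Before purchase:

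1. Obtain the fermented product's ingredients and approximate proportions from the local producer.
2. Make up the comparator from store-bought acid-pickled forms of the same vegetables in about the same proportions. Staff already portion the food. Use sauerkraut alone only if the fermented product is cabbage alone.
3. State both compositions under Vegetables preparation, and align the comparator line in Project budget with them.
4. Word the conclusion as fermented product versus acid-pickled product, since source and acidifying process differ even after matching.

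If food has already been supplied, documenting both compositions and applying item 4 is still worthwhile.

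The cost is some sourcing work and a possible price change on the $355 line, which the documents do not price. Assumed rises of 10%, 50% and 100% would add $35.50, $177.50 and $355, or 0.24%, 1.19% and 2.37% of $14,975.65. No unallocated amount is available to absorb this, and the documents do not show that matching store products can be had. If the fermented product proves to be cabbage alone, only wording changes.
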